5. STUDY OUTCOMES

5.1 **Primary Outcome**

The primary outcome will be the perceived change of dyspeptic symptoms assessed by the Leuven Dyspepsia Questionnaire (LDQ) between visit 1 (off treatment) and 3 (after treatment). The questionnaire contains 3 domains/questions which related to: a) The inability to finish a meal due to early satiety b) The feeling of food lying heavily in the stomach c) Feeling bloated in the stomach. The questionnaire is presented to the patients in the form of three questions which define five grades of severity (0-4), and which are supported by pictograms expressing the associated severity. Higher total scores indicate more severe dyspeptic symptoms. For each subscale 0 normal, 1 mild dyspepsia; 2, moderate dyspepsia; 3, severe dyspepsia; 4, very severe dyspepsia. The questionnaire is to be evaluated on a daily basis and the mean of the values of the three symptoms is proposed to represent the severity of that day. A weekly score can be calculated from the daily scores and is currently proposed for the primary use of the scale.(21)

The LDQ has been developed using standard methods, including focus group interviews and cognitive debriefing interviews.(21) The further validation of the score was undertaken with the means of interventional studies, evaluating the response of this questionnaire to prokinetic and neuromodulatory medications. The LDQ has shown to be a good rating scale to be used as a severity indicator of dyspepsia and can be given to the same patient in subsequent sessions to track the change in symptoms. A minimally clinically important difference has also been determined. The results of this validation work have been published in peer reviewed journals.(22, 23)

The Leuven Postprandial Distress Scale, which is supported by the European Medicines Agency, is a sensitive and reliable patient-reported outcome instrument to assess symptoms in the functional dyspepsia/postprandial distress syndrome. Based on this information, the LDQ variable will be the main result to verify whether the test medication in this trial is efficacious. In this open-label study in which placebo and treatment effects are summed we expect a moderate to large >60% reduction in mean symptom burden as measured by the LDQ (results will be shown as mean \pm SD).

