	Amara Drops will be dispensed with 10-20 drops (0.25-0.50ml) taken three times a day prior to meals for 4 weeks. Patients are free to vary the dose between these limits as considered appropriate. The amount taken will be monitored by checking the volume remaining in the bottle at the end of the 4-week intervention. During this time, patients will continue reporting the presence and severity of dyspeptic symptoms and any side effects into the app.
	At the end of the study period (Study Visit #3) the questionnaires including LCT and the ¹³ C-breath test measurement with concurrent high-resolution electro-gastrography (Gastric Alimetry System) and heart rate monitoring plus concurrent assessment of visceral sensitivity will be repeated. Additionally, the patients will be asked if their global satisfaction was better on Amara treatment, whether they wish to continue treatment and /or recommend the treatment to others with similar symptoms. Questionnaires and diary entries on side effects are also available as paper version.
Risk / Benefit Assessment	The initial assessment of patients with functional dyspepsia will adhere to international guidelines on the investigation of this condition. Amara Drops (Weleda) is a proprietary preparation that has been marketed over the counter (OTC) for many years. No serious side effects have been reported. ¹³ C-breath test gastric emptying studies and other measurements of gastric function (e.g. electro-gastrography) are indicated in patients with functional dyspepsia that do not respond to first-line, dietary management, and empirical treatment. These tests are non-invasive and not radioactive and is associated with no adverse outcomes. Clinical validation studies report that the intake of the 400ml (300kcal) Nottingham Test Meal is tolerated by all healthy controls and >95% of patients with functional dyspepsia without inducing vomiting.
Objectives:	The aim of the present study is to find out if the regular intake of Amara has effects on the perceived symptom burden reported by patients with functional dyspepsia. Since dyspeptic symptoms may be associated with abnormal gastric motor and sensory function, these aspects will be assessed by validated methods.

Outcomes:	 Primary objective / outcome measure: change in perceived symptom burden during regular intake of Amara assessed by the Leuven Dyspepsia Score between visit 1 (off treatment) and 3 (on treatment).

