Study Schedule:	Month Year of First-Participant-In (planned): July 2022 Month Year of Last-Participant-In (planned): August 2024 Month Year of Last-Participant-Out (planned): September 2024
Investigator:	[name]. med. [name]
investigator.	Leitender Arzt, Zentrum für Integrative Gastroenterologie
	Leiter, Magen Darm Funktion: Basel, Labor und Klinik für funktionelle Magendarm Erkrankungen und Motilitätsstörungen
	[contact]
	[contact]
Study Centre:	Single Centre, Clinic Arlesheim (CLA), [name]

Statistical Considerations:	Differences between the scores from the primary and secondary outcome measurement variables – at baseline (following run-in) and after either 4- weeks treatment - will be compared initially by t-test if the data is normally distributed and Wilcoxon rank sum test when data are not normally distributed. In addition, we will perform univariate and multivariate linear regression analysis in which potential covariates will be considered; confounding will be evaluated by adding these variables to the linear regression model and looking at the change of the regression coefficients. These variables will include participants' gender, age, perceived symptom severity and gastric function at baseline.
	In the analysis of the primary outcome two-tailed $p \le 0.05$ will be considered statistically significant. Since the evaluation of the secondary endpoints is purely exploratory, other p-values will be calculated but reported without claiming significance,
GCP Statement:	This study will be conducted in compliance with the protocol, the current version of the Declaration of Helsinki, the ICH-GCP as well as all national legal and regulatory requirements.

ABBREVIATIONS

13C BT	¹³ C Acetate Breath Test
AE	Adverse Event
BASEC	Business Administration System for Ethical Committees, (https://submissions.swissethics.ch/en/)
CA	Competent Authority (e.g. Swissmedic)
CEC	Competent Ethics Committee
ClinO	Ordinance on Clinical Trials in Human Research (in German: KlinV)
CRF	Case Report Form
CTCAE	Common terminology criteria for adverse events
DSUR	Development safety update report
eCRF	Electronic Case Report Form
EKNZ	Ethikkommission Nordwest- und Zentralschweiz
HADS	Hospital Anxiety and Depression Scale
GCP	Good Clinical Practice
HRA	Federal Act on Research involving Human Beings (in German: HFG)
HRV	Heart Rate Variability
IB	Investigator's Brochure
IBS-SSS	Irritable Bowel Syndome Symptom Severity Score
ICS	Internal Coherence Scale

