ШΤ	Investigator-initiated Trial
KLA	Klinik Arlesheim
LCT	Lüscher Colour Test
LDQ	Leuven Dyspepsia Questionnaire
NTM	Nottingham Test Meal
OTC	Over The Counter
PHQ-12	Patient Health Questionnaire 12-items, depression module
PI	Principal Investigator
RCT	Randomised Controlled Trial
RDQ	Reflux Disease Questionnaire
SAE	Serious Adverse Event
SDV	Source Data Verification
SOP	Standard Operating Procedure
SPC	Summary of product characteristics
SUSAR	Suspected Unexpected Serious Adverse Reaction
TMF	Trial Master File

STUDY SCHEDULE

Study Periods	Screening	Physiological Measurement and Treatment	Physiological Measurement and End
Visit	1	2	3
Time (days)	Ca14-28d	1	28±14d
Medical History and Demographics	x		
Leuven Dyspepsia Questionnaire (LDQ)	x		x
Screening questionnaires	x		
Pregnancy test (urine)	x	(x)	
In-/Exclusion Criteria	x		
Patient Information and Informed Consent	x		
Primary Outcome Measure: LDQ total score	x		x
Secondary Outcome Measure: other GI symptom questionnaires	x	x	x
Lüscher Colour Test	x	x	x
Physiological Measurement (13C BT, HRV)		x	x
Intake of the Study Medication (Amara Drops)		x	x
Compliance with therapy			x
Satisfaction with therapy / Whether a prescription of Amara is wanted			x
Concomitant Medication, Therapy	x	x	x
Serious Adverse Events	x	x	x

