4. STUDY OBJECTIVES

4.1 Overall Objective

The purpose of the present study is to evaluate whether the herbal drug Amara improves the subjective, perceived burden of abdominal symptoms in patients with functional dyspepsia. It will also assess if the treatment is well tolerated. The present study will also investigate psychological and physiological function. This additional information should provide insight into which patients benefit the most from the treatment with Amara. The results of this prospective, open-label therapeutic study will also inform the study design for any subsequent RCT study in functional dyspepsia.

4.2 **Primary Objective**

Document perceived changes in upper gastrointestinal, dyspeptic symptoms reported by patients with functional dyspepsia treated with Amara for 4 weeks, as assessed by the Leuven Dyspepsia Score between visit 1 (off treatment) and 3 (after treatment)..

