9. STUDY ASSESSMENTS

9.1 Study flow chart(s) / table of study procedures and assessments

9.2 Assessments of outcomes

The primary study outcome of dyspeptic symptoms will be assessed by the LDQ three times (screening, baseline, study completion).

Secondary study outcomes will be assessed (i) by other validated questionnaires assessing gastrointestinal and psychological comorbidity as well as (ii) by physiological measurement of gastric motor and sensory function using the NTM Drink Test with ¹³C measurement of gastric emptying (section 5). Additionally, the Lüscher Colour Test will be performed to assess the psychological state and personality profile potentially changing during treatment (section 5.3).

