11.2 Determination of Sample Size

In this prospective open label study, placebo effects are likely to be present. Previous randomized controlled trials of therapy in functional gastrointestinal disorders indicate that this can be present in up to 40% of patients.(15) To compensate for this confounding factor and to demonstrate convincing

changes in perceived symptom burden at least 60% of patients should show improvement on-treatment compared to off-treatment (run-in phase). Assuming a moderate effect (Cohen's effect size of 0.4) on the primary outcome measure (effect size and standard deviation as in a previous paper by Carbone et al. (21)) power calculation suggests that 58 patients are required to detect a significant effect at a convincing level of statistical significance (beta 0.9, alpha <0.05). In the context of this study, the inclusion of 60 patients should also be sufficient to inform the design of any, future randomized, placebo-controlled study.

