11.5 Handling of missing data and drop-outs

Participants who filled out only the screening and/or only the first questionnaire (baseline) will be defined as dropouts. These dropouts will be replaced.

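### The primary outcome has two contradictory baselines, and the visit 1 version measures change from the same score that qualifies patients for entry

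*Protocol*

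**What the plan says.** **Visit 1 as baseline.** Section 5.1 takes the change "assessed by the Leuven Dyspepsia Questionnaire (LDQ) between visit 1 (off treatment) and 3 (after treatment"). The synopsis (Outcomes) has the change "assessed by the Leuven Dyspepsia Score between visit 1 (off treatment) and 3 (on treatment"), and section 4.2 repeats "between visit 1 (off treatment) and 3 (after treatment"). In the Study Schedule the row "Primary Outcome Measure: LDQ total score" is marked at visits 1 and 3 and left empty at visit 2.

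**After the run-in as baseline.** The synopsis (Statistical Considerations) compares primary and secondary scores "at baseline (following run-in") with those after four weeks of treatment. Section 9.2 has the primary outcome "assessed by the LDQ three times (screening, baseline, study completion"). The sample-size argument in 11.2 requires that "at least 60% of patients should show improvement on-treatment compared to off-treatment (run-in phase"). Section 11.5 treats screening and baseline as different forms: "Participants who filled out only the screening and/or only the first questionnaire (baseline) will be defined as dropouts".

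**Unresolved.** Sections 11.1 and 11.4 speak only of baseline. Section 11.4.3 refers to the beginning of the study.

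Visit 1 is the screening visit. Sections 7.2 and 9.3.1 use the LDQ taken there as the entry instrument: at least 2 of 4 on two or more subscales, total at least 4. Sections 3.5 and 6.1 justify the 2–4 week run-in as protection against regression to the mean.

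**The concern.** The two definitions give different primary results from the same patients. A site that follows the schedule would not collect the visit 2 LDQ that the synopsis statistics and section 9.2 need, and no later analysis document could recover it.

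The visit 1 definition also has a bias of known direction. Patients enter only if their LDQ is high enough on that day, and change is then measured from that same score. Whenever the retest correlation is below 1, the average falls with no treatment or placebo effect at all. The run-in comes after this measurement, so it cannot protect the primary comparison, and a single-arm study has no control group to absorb the fall.

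At stake are the two-sided 5% test in 11.4 and the effect size that 11.1 wants for planning the next study.

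**Working it through.** **1. The texts side by side.** The schedule provides two LDQs (visits 1 and 3); section 9.2 requires three. The synopsis outcome starts the comparison before the run-in; the synopsis statistics start it after. Both cannot describe one endpoint.

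**2. Inputs.**
- From the protocol: three items scored 0–4; the entry rule above; 60 completers (7.4); two-sided 5% test (11.4); planned standardised effect 0.4 (11.2).
- Not in the protocol, so assumed: latent retest correlation 0.5–0.9, and the share of assessed patients who pass the cut-off.

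**3. The plan's own figures.** The protocol gives no figure for this bias. Its 58 patients can be recovered with a one-sided 5% test and 90% power: ((1.645 + 1.282)/0.4)² = 53.5, so 54; 55 with the t distribution; 55/0.955 = 57.6, so 58 with Wilcoxon efficiency. The two-sided t-test needs 68. That is a separate matter; only the 0.4 is used here, as a yardstick.

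**4. Direction and order of size by formula.** Let the scores at visits 1 and 3 be standard normal with correlation ρ, and let entry require a visit 1 score above c. With λ = φ(c)/(1 − Φ(c)):
- mean fall = (1 − ρ)λ
- variance of change = (1 − ρ)²(1 + cλ − λ²) + 1 − ρ²

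For c = 0 (50% pass) and ρ = 0.7:
- λ = 0.798, so the fall is 0.3 × 0.798 = 0.239 SD.
- The variance is 0.09 × 0.363 + 0.51 = 0.543, so the SD is 0.737.
- d = 0.239/0.737 = 0.325, and the chance of a significant improvement at n = 60 is 70%.

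For c = −1 (84% pass) and ρ = 0.7: fall 0.086 SD, d = 0.115, chance 14%.

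**5. Simulation on the actual scale.** Three latent normal items (SD 1, inter-item correlation 0.5) were rounded and clipped to 0–4 at three visits, with no treatment effect and the protocol's entry rule applied at visit 1. There were 400,000 patients per scenario and 6,000 resampled trials of 60, each analysed with a paired t-test. Rejection rates for visit 1 to visit 3:

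| Share passing | r = 0.5 | 0.65 | 0.8 | 0.9 |
|---|---|---|---|---|
| 50% | 91% | 79% | 56% | 36% |
| 59% | 76% | 62% | 40% | 27% |
| 80% | 32% | 24% | 16% | 11% |
| 90% | 13% | 10% | 9% | 7% |
| 96% | 7% | 6% | 6% | 5% |

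The spurious fall is 0.03–0.99 points on the 0–12 total, a standardised change of 0.03–0.43 against the planned 0.4. Noncentral-t check at n = 60: d = 0.04 gives 6%, 0.20 gives 33%, 0.44 gives 92%.

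**6. Visit 2 as baseline, same patients.** Rejection is 4–6% if fluctuation at visits 1 and 2 is independent. With autocorrelation of 0.2, 0.4 and 0.5 it rises to at most 9%, 13% and 16%. If the entry cut-off were applied again to the visit 2 score, selection would return: 5–71% over the whole grid, 9–22% at an 80% pass rate.

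**The case against.** **The text is lopsided.** Every passage that formally defines the outcome or objective uses visit 1. Sections 6.1 and 9.3.1 describe two steps within visit 1 (screening forms, then questionnaires after consent or inclusion), so 11.5, and perhaps the three assessments in 9.2, could both lie within that visit. The run-in remark in 11.2 concerns a share of improvers, not the baseline of the mean score. This weakens some of the support, but the synopsis statistics still place the baseline after the run-in and conflict openly with 5.1. A second LDQ on the screening day would also reflect nearly the same symptom state, so the bias would remain.

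**The size is assumed, and may be small.** Section 7.2 applies the LDQ after the physician has diagnosed functional dyspepsia, so a high pass rate is plausible. At 80–96% the rejection rate is 5–32%. Section 5.1 expects a reduction above 60%; a spurious fall of 0.12–0.45 points on an entry mean of 7.4 (80% pass) is only 2–6%. This stands: the upper end of the range should not be read as the expected size.

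**Efficacy is disclaimed.** The hypothesis in 11.1 is about change, not about Amara. Section 6.1 concedes a large placebo response and says the design cannot evaluate efficacy. This limits the consequence. But the concession concerns placebo response; against regression to the mean the protocol claims a safeguard, and the visit 1 definition bypasses it. Section 5.1 also makes the LDQ the result that is to show whether the medication works.

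**Repeat selection at visit 2 is hypothetical.** The schedule checks eligibility only at visit 1. Agreed; it matters only because 7.4 leaves the point open.

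**Conclusion.** The concern holds. The protocol defines the primary baseline in two incompatible ways, and section 11 does not settle it. Under the visit 1 definition the comparison is biased towards improvement, and the run-in plays no part in it.

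The direction follows from the design. The size cannot be fixed from the documents: with no true change, rejection ranges from about 5% (96% pass) to 91% (50% pass, retest correlation 0.5), and the spurious standardised change from 0.03 to 0.43. These figures assume the item model above and fluctuation that is independent between visits. They leave out the tendency to present at a symptom peak, which section 3.5 names and which would add to the fall.

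A baseline after the run-in reduces this bias. It does not remove it for certain, and it does nothing about placebo response. Because the primary result depends on which definition is used, this must be settled in the protocol.

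**What to change.** - Define one baseline, measured after the run-in and before the first dose. It can be the LDQ at visit 2, or the last run-in week of daily scores if the app carries the LDQ items (5.1 says a weekly score is proposed for the scale's primary use). Compare it with the same measure at the end of treatment.
- If visit 2 is chosen, add the LDQ to that column of the schedule.
- Bring the synopsis outcome, the schedule, 4.2 and 5.1 into line with the synopsis statistics, 9.2, 11.2 and 11.5. In 11.1, 11.4 and 11.4.3, name the visit instead of leaving the baseline open.
- Keep the visit 1 LDQ for eligibility, and report the visit 1 to visit 2 change as off-treatment drift.
- State whether the discontinuation rule in 7.4 covers the LDQ cut-off, and reconcile it with the chosen baseline. Selecting again on the visit 2 score would bring the bias back.

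The cost is a wording amendment plus three questions at an existing visit, which 9.2 already assumes, or use of diary data already being collected. No extra patients or visits are needed. The observed improvement may turn out smaller.

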An appointment will be made 2-4-weeks later for the second study visit at which time the ¹³C gastric emptying study will be performed again. The run-in period is 2-4-weeks. This reduces the influence of spontaneous "regression to the mean" (i.e., false positive results).(15)

Gastric motor and sensory function will be assessed by ingestion of the 400ml, 300kcal Nottingham Test Meal (NTM) labelled with ¹³C acetate. This provides both an assessment of patient symptoms / visceral sensitivity to gastric filling with the 400ml liquid nutrient meal and also an assessment of gastric emptying. The 400ml NTM can be ingested by >95% of patients with functional dyspepsia.(19,

24) The ¹³C isotope is not radioactive, it takes 2-hours to complete and this technique is very appropriate for repeated assessment of gastric emptying.(16) In a subset of 20 consecutive patients, gastric electrical activity will be measured before, during and after ingestion of the Nottingham Test Meal using the non-invasive Gastric Alimetry System (high-resolution gastric mapping / electro-gastrography). Concurrent heart rate monitoring will provide an assessment of cardiovagal tone / autonomic nervous function.

The treatment period with Amara drops is four weeks per patient; participants will be instructed to take 10-20 drops of the herbal medicine Amara three times a day before meals over 28 days. This treatment period is in accordance with previous studies for aromatic bitter substances and represents the minimum recommendation for study duration in functional gastrointestinal disorders.(15) During the treatment period patients will record their symptoms using a mobile application (reminder will be sent at 21:00 every day). In addition, patients can note side effects that they perceive to be caused by Amara. If participants do not regularly provide this information, then a team member will call to ask if they have any problems.

At the end of the treatment period the participant will return to Clinic Arlesheim for repeat assessment. The LDQ and other patient related outcomes will be assessed again and ¹³C gastric emptying study will be repeated on treatment.

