9.3 Procedures at each visit

9.3.1 Screening visit

At the orientation consultation/screening visit the investigator will review the case notes, investigation results (e.g., laboratory tests, gastroscopy) and interview the patient to ensure that inclusion and exclusion criteria are met. In order to comply with the inclusion criteria, pregnancy tests will be performed on all women of childbearing age. At the screening visit, the LDS and HADS questionnaires will be completed at the time of recruitment and used as screening instruments. This data will be collected using an on-line application. After inclusion, further health-related questionnaires will be completed and

the Lüscher Color Test will be performed.

A time is booked 2-4 weeks later for the second study visit. A mobile application will be downloaded onto the personal smart phone device (Symptom Tracker, Gastric Imaging & Analysis GmbH). Paper forms are available if required. During the 2-4 week "run-in" period patients will document their symptoms every day using a mobile application. A reminder will be sent to complete this electronic form every day at 21:00.

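### The primary outcome compares a single LDQ at screening with a single LDQ at visit 3, although section 5.1 proposes a weekly score from daily ratings and the run-in exists to supply a later baseline

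*Protocol*

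**What the plan says.** **Outcome.** Section 5.1 defines the primary outcome as the change in dyspeptic symptoms "assessed by the Leuven Dyspepsia Questionnaire (LDQ) between visit 1 (off treatment) and 3 (after treatment". The Study Schedule table lists "Primary Outcome Measure: LDQ total score" and marks it at visits 1 and 3 only.

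**Scoring.** The same section 5.1 says: "The questionnaire is to be evaluated on a daily basis and the mean of the values of the three symptoms is proposed" as that day's severity. It then adds: "A weekly score can be calculated from the daily scores and is currently proposed for the primary use of the scale".

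**Daily records.** For the run-in, section 9.3.1 says that "patients will document their symptoms every day using a mobile application". For treatment, section 6.1 says: "During the treatment period patients will record their symptoms using a mobile application (reminder will be sent at 21:00 every day". Sections 11.4 and 11.4.2 compare questionnaire scores at baseline and after four weeks. No section gives the daily records a role in the primary outcome.

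**Baseline.** Section 7.2 uses the screening LDQ as the entry test: at least 2 of 4 on at least two subscales, total at least 4. Section 3.5 justifies the 2-4 week run-in by the need to limit regression to the mean, and section 6.1 repeats this. The synopsis (Statistical Considerations) places baseline after the run-in, and section 11.2 expresses improvement relative to the run-in phase. Section 9.2 says: "The primary study outcome of dyspeptic symptoms will be assessed by the LDQ three times (screening, baseline, study completion".

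**The concern.** There are two problems in one definition.

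First, the outcome does not use the scale in the form that section 5.1 puts forward for primary use. If each visit score reflects a single day, all of the day-to-day variation in postprandial symptoms enters the paired difference. That would inflate the SD of change and cost power.

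Second, the baseline is the score on which patients were selected. Patients who pass a severity threshold partly because of a bad spell will tend to score lower later without any treatment. In a single-arm study, that fall is counted in the primary change. The run-in was introduced to let it happen before baseline, but a visit 1 baseline starts the comparison before the run-in begins.

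**Working it through.** **1. The plan's own figure.** Inputs from section 11.2: d = 0.4, power 0.90 (written as beta 0.9), alpha 0.05, n = 58. Section 11.4 makes the test two-tailed. Section 3.8 and the synopsis give alpha 0.01.

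For a paired mean change, n = ((z for alpha + z for power) / d)².

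- Two-sided 0.05: ((1.960 + 1.282) / 0.4)² = 65.7, so 66; 68 by exact t.
- Two-sided 0.01: (3.857 / 0.4)² = 93.0, so 93; 97 by exact t.

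So 58 does not follow from the stated two-sided inputs. Exact t power at d = 0.4 and two-sided 0.05 is 0.850 at n = 58 and 0.862 at n = 60. That is a separate matter, but it shows that the design has no spare power.

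**2. What averaging would do, if the visit score is a single-day score.** Let rw be the correlation between two days in the same week and rb the correlation between a run-in day and a treatment day. With equal variances and exchangeable days,

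Var(change of 7-day means) / Var(change of single days) = [rw + (1 − rw)/7 − rb] / (1 − rb).

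The Protocol gives neither correlation. The assumed ranges are rw 0.4 to 0.9 and rb 0 to 0.75 times rw. Example with rw 0.5 and rb 0.25: (0.5 + 0.0714 − 0.25) / 0.75 = 0.429. The SD ratio is √0.429 = 0.655 and d becomes 0.40 / 0.655 = 0.61.

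| rw | rb | SD ratio | d | Power, n = 58, two-sided 0.05 |
|---|---|---|---|---|
| 0.4 | 0.30 | 0.515 | 0.78 | >0.99 |
| 0.5 | 0.25 | 0.655 | 0.61 | 0.996 |
| 0.7 | 0.35 | 0.777 | 0.51 | 0.971 |
| 0.8 | 0.40 | 0.845 | 0.47 | 0.943 |
| 0.9 | 0.45 | 0.919 | 0.44 | 0.903 |
| 0.9 | 0 | 0.956 | 0.42 | 0.879 |

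A different model, with a separate term for individual response, has Var = 2(1 − ρ) + h for single days and 2(1 − ρ)/k + h for weekly means. Here ρ is the day-to-day correlation, h the variance of individual response as a share of daily variance, and k the effective number of independent days. With ρ 0.4 to 0.8, h 0.2 to 0.5 and k 3.5 to 7, the extremes are:

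- ρ 0.4, h 0.2, k 7: √(0.371 / 1.40) = 0.515
- ρ 0.8, h 0.5, k 3.5: √(0.614 / 0.90) = 0.826

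This lies inside the range above.

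**3. The reverse case.** Section 11.2 takes d = 0.4 from the scale's validation paper, which section 5.1 also cites for the weekly score. If 0.4 is a weekly-score effect and the visit form covers one day, the visit-based d is 0.4 times the SD ratio. For rw 0.5 to 0.8 with rb half of rw, that is 0.26 to 0.34. Power at n = 58 is then 0.50 to 0.72, and 94 to 156 patients are needed for 90%. The Protocol does not say which case applies.

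**4. Total or mean.** Section 5.1 mixes a total with a mean of three items. The total is three times the mean, so this alone changes neither d nor power. What differs is one completion against seven days.

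**5. Baseline, side by side.**

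| Place | LDQ baseline |
|---|---|
| Sections 4.2 and 5.1 | Visit 1, off treatment |
| Study Schedule | Visit 1; no LDQ at visit 2 |
| Synopsis, Statistical Considerations | After run-in |
| Section 11.2 | Run-in phase |
| Section 9.2 | Screening and baseline are separate assessments |

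These cannot all hold. Only the first two make the selection score the baseline, and they are the ones that define and schedule the outcome.

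**The case against.** The strongest objection is that the single-day premise is not documented. The questionnaire is in an appendix that is not shown, and no section states its recall period. The limitations in section 6.1 contrast drink tests with questionnaires on the ground of patient recall, which suggests that the forms look back over some period. If the visit LDQ already asks about the past week, much of the gain in step 2 disappears. This stands: the gain is conditional.

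Section 5.1 also says that the LDQ can be given at successive sessions to track change, and it calls the weekly score proposed, not required. So visit-based use is not invalid in itself. That stands too, but the stated preference for primary use remains unfollowed and unexplained.

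A reader might infer that precision is being discarded from data already in hand, with power going from 86% at d = 0.40 to 97% at d = 0.50. The documents do not support this. The app records the presence and severity of dyspeptic symptoms, but nothing says that it uses the three LDQ items. The correlations are assumed, and d = 0.40 may not be a single-day effect.

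Finally, greater precision does not remove the placebo response from an open, uncontrolled study whose limitations say that it cannot evaluate efficacy, and an LDQ at visit 2 would repair the baseline without any diary. Both are fair. The second concedes that the baseline needs repair.

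**Conclusion.** The point holds as a conflict over how the primary outcome is measured, with a probable but unquantified loss of precision. The text itself establishes four things: the outcome departs from the scoring that section 5.1 proposes for primary use; the daily records play no part in it; its baseline is the entry score taken before the run-in; and the sections disagree on the timing and number of LDQ assessments. Regression to the mean is a bias in the primary change whatever the recall period, but its size cannot be computed because no score SD or retest correlation is given.

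The precision gain, with an SD ratio of about 0.5 to 0.96 and power rising from about 0.85 to between 0.88 and over 0.99 at 58 to 60 patients, rests on assumed correlations, a single-day visit form and a single-day d of 0.40. It should be read as a range under those assumptions and not as a finding about this trial. The change is worth making but is not indispensable.

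**What to change.** - State that the daily app form contains the three LDQ items, and state the recall period of the visit LDQ.
- Define the primary outcome as the mean daily LDQ score over the last 7 treatment days minus that over the last 7 run-in days. Add a minimum-days rule, for example at least 4 of 7 in each week.
- Keep the visit 1 to visit 3 change in total score as a sensitivity analysis.
- If the app items differ from the LDQ for patients already enrolled, do not split the primary outcome across two instruments. Keep one visit-based LDQ outcome for everyone, with the baseline taken after run-in at visit 2 where it was collected, as section 9.2 describes. Prespecify the weekly diary score as supportive. Where no visit 2 LDQ exists, say that regression to the mean is not controlled.
- Reconcile the synopsis, Study Schedule, section 5.1 and section 9.2 on which score, which visits and which baseline apply, and say whether d = 0.4 refers to a weekly or a single score.

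Cost: a protocol amendment with ethics committee approval under section 2.10 if substantial, possibly a change to the app form, and missing diary days to handle. No extra visits or patients are needed. Version 1.4 is dated November 2023 and first inclusion was planned for July 2022, so the choice for patients already enrolled should be fixed before their outcome data are examined.
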